1.3 Summary of Results of Belatacept Investigational Program

Given belatacept was an investigational agent when the first version of this trial began, comprehensive information regarding its use to date is provided in Appendix C. A summary of this information is provided, in brief, below.

1.3.1 Preclinical Data

Both belatacept and its parent molecule CTLA4-Ig have been studied extensively in vitro and in non-human primates by the PI and others including Emory transplant investigators. A comprehensive list of the pertinent findings from pre-clinical studies is available in Appendix C and in the IB. These data are summarized below.

Pre-Clinical Safety

Although belatacept has increased binding affinity for B7 molecules in primates and humans compared to CTLA4Ig, the binding affinity for murine CD80 and CD86 is lower. Since CTLA4Ig binds more avidly than does belatacept in mice and it is very similar to belatacept in both its mechanism of action and its structure, CTLA4Ig is considered an acceptable homologue for belatacept for rodent toxicology assessments to support registration requirements. CTLA4Ig was not found to be mutagenic or clastogenic in mice but was shown to increase the risk of virally driven malignancies consistent with its known immunosuppressive properties.

Non-clinical safety assessments of belatacept were performed in cynomolgus monkeys and showed that it was well tolerated when given intravenously to monkeys at doses up to 50 mg/kg every other day for 1 month (15 doses) or once weekly for 6 months. Belatacept was not found to be mutagenic or clastogenic in cynomolgus monkeys. The major non-clinical findings in monkeys with belatacept were reversible, related to the pharmacology of the drug, and consisted of minimal decreases in serum IgG levels and minimal-to-moderate lymphoid depletion of germinal centers in the spleen and/or lymph nodes at all dose levels. There were no solid or lymphoid malignancies noted in the 6 month toxicity study with belatacept or in a 1 year toxicity study with CTLA4-Ig. Additional pertinent findings are summarized in Appendix C; a more thorough description of these studies is available in the IB.

Pre-Clinical Efficacy

Belatacept shows greater binding avidity than its parent molecule CTLA4Ig for human CD80 and CD86. It is approximately 10-fold more effective in vitro on a per-dose basis than CTLA4Ig at inhibiting T-cell proliferation, T-cell cytokine production, and CD28-dependent killing of target cells by natural killer-like cells. In an in vivo primate immune response model, belatacept potently blocked a primary antibody response against sheep red blood cells. At equivalent doses, belatacept was 3- to 11-fold more potent (by ID₉₀) than CTLA4Ig at blocking specific humoral responses.

Belatacept was found to be efficacious for the prevention of graft rejection in a cynomolgus monkey model of renal transplantation.³⁷ Belatacept monotherapy was

superior to a regimen of CsA + corticosteroids in the prolongation of graft survival in this stringent model. A regimen of belatacept + MMF + corticosteroids and a regimen of belatacept + basiliximab prolonged graft survival superior to belatacept monotherapy as well as that historically observed in monkeys treated with CsA + corticosteroids. Analysis of pharmacokinetic (PK) data in monkeys suggested a relationship between trough serum drug concentrations and immunosuppressive efficacy. Additional pertinent findings are summarized in Appendix C; a more thorough description of these studies is available in the IB.

1.3.2 Clinical Pharmacology

Single-dose Phase 1 studies with belatacept were performed in 40 healthy volunteers using doses ranging from 0.1 to 20 mg/kg. No deaths or serious adverse events (SAEs) were reported. All reported clinical AEs were of mild or moderate intensity. No histamine-like peri-infusional AEs were reported. There was no evidence for the development of anti-belatacept antibodies. Belatacept kinetics were found to be dose-proportional between 1 and 20 mg/kg. The half-life was adequately characterized between the 5 and 20 mg/kg dose levels, and ranged between 176 – 210 hours (7-9 days). The steady-state volume of distribution (VSS) values were small, indicating that the drug (with high molecular weight) was confined mainly in the plasma and extracellular space. Overall, the PK of belatacept appears to be linear following i.v. administration in healthy subjects. Additional pertinent findings are summarized in Appendix C; a more thorough description of these studies is available in the IB.

1.3.3 Phase 2 Study in Rheumatoid Arthritis

Study IM103002 was a Phase 2 pilot study that assessed the efficacy, safety, and immunogenicity of multiple i.v. doses of belatacept, CTLA4Ig, and placebo in 214 subjects with RA. Eligible subjects had a diagnosis of RA for ≤ 7 years had failed at least 1 disease-modifying anti-rheumatic drug therapy, including etanercept, and had active disease (≥ 10 swollen joints, ≥ 12 tender joints, an erythrocyte sedimentation rate ≥ 28 mm/h, and morning stiffness ≥ 45 minutes). Overall, belatacept demonstrated dose-dependent efficacy in this subject population, as evidenced by American College of Rheumatology scores. With respect to safety, no deaths were reported during the treatment or follow-up period (through Day 169), and no SAEs were considered drug related by the investigators.

1.3.4 Phase 2 Study in Solid Organ Transplantation

Study IM103100 was a 1-year, partially-blinded, randomized, active-controlled, multiple-dose, multicenter (including Emory) non-inferiority study in de novo renal transplant recipients.³⁶ All subjects received basiliximab induction and background maintenance immunosuppression with MMF and corticosteroids. Subjects were randomized in a 1:1:1 ratio to treatment with belatacept (more intensive [MI] or less intensive [LI] regimens) or CsA. Belatacept was administered in a double-blind fashion, with the investigator and subject blinded to the identity of the belatacept dose regimen. The MI regimen most closely approximates that proposed in this trial.

The dosing schedule, evaluation criteria, and efficacy results for Study IM103100 study are presented in Appendix C. Overall, the mean duration of exposure was comparable across all 3 treatment groups. Specifically, mean duration of exposure was 300, 308, and 294 days in the belatacept MI and LI groups and the CsA group, respectively. The overall histological severity grade of acute rejection episodes and the average number of rejection episodes per subject appeared to be similar across the 3 treatment groups. By month 12, chronic allograft nephropathy (CAN) was approximately 30%-50% less common with belatacept than with CsA. Death and/or graft loss occurred infrequently in all treatment groups, and was least frequently reported in the belatacept LI group. Most graft losses occurred for technical, rather than immunological reasons. With respect to safety, the rate of AEs, including AEs resulting in discontinuation, was similar across the 3 treatment groups. The rate of SAEs was somewhat higher for both belatacept treatment groups than for the CsA treatment group. As described in Appendix C, this difference is due to an increased number of reports of AEs of transplant rejection that were not subsequently confirmed as transplant rejection, in the belatacept treatment groups.

Topics of special interest, including the assessment of renal function, cardiovascular and metabolic effects, and an exploratory analysis in an extended criteria donor population or in subjects with impairment of renal function post-transplant, is presented in Appendix C.

1.3.5 Clinical Results from the Ongoing Trial.

In keeping with the study plan proposed in the initial funding cycle, we have conducted and preliminarily reported¹ a prospective, randomized trial to determine whether a single dose of alemtuzumab permits patients to avoid both CNIs and steroids, and instead be transplanted on a belatacept/sirolimus-based regimen. The trial was designed to offer patients the opportunity to wean from sirolimus at 1 year, and if stable, consider weaning off all immunosuppression thereafter. Randomization occurred with regard to whether patients received a single dose of unfractionated donor bone marrow (10^8 nucleated cells/kg) on day 7. Enrollment was completed, with 20 participants participating. All were non-sensitized (crossmatch negative, PRA<20%) recipients of live donor kidneys enrolled in an IRB-approved (IRB# 5064), prospectively registered (ClinicalTrials.gov Identifier: NCT00565773) trial. Induction immunosuppression consisted of intraoperative alemtuzumab (30mg IV), with three daily doses of methylprednisolone (500mg) followed by steroid elimination on day 3. All patients received and tolerated the intended induction dose. Maintenance immunosuppression consisted of belatacept (10mg/kg IV on days 1, 3, 7, 14, q2w x 4, q month x 3, 5mg/kg monthly) and sirolimus (adjusted to trough levels of 8-12ng/ml x 6 months, then 5-8ng/ml). All patients tolerated belatacept. Four patients developed arthralgias, edema or mouth ulcers requiring conversion from sirolimus to MMF.

Twenty patients (median 45 years, range 20-69; 12 male:8 female, 16 Caucasian:4 African American, all EBV seropositive) have been transplanted. In general, alemtuzumab induction followed by a belatacept-based maintenance regimen has been well tolerated and prevented rejection. With a mean follow-up of >700 days (102-1345 days), all patients have excellent graft function. Mean creatinine in mg/dl (range; n having reached that time point) at 6, 12 and 24 months is 1.1 (0.7-1.9; n=19), 1.1 (0.9-1.9; n=19) and 1.2 (0.6-1.8; n=11) respectively. No patient was chimeric after bone marrow infusion, and there have been no differences in outcome attributable to the infusion

indicates to us that complete immunosuppressive weaning offers an unacceptable risk and we have accordingly altered our protocol to eliminate this as an explicit goal of the trial. It is important to point out that our approach in this situation is substantially different from that taken by the investigators of a recently reported tolerance trial.^{2,109-111} In this trial performed at the Massachusetts General Hospital (MGH), several patients have been weaned from all immunosuppression. However, ABMR led to graft loss in 2 of 10 patients, and DSA formed in several other patients that have been followed expectantly. Endothelial injury has been observed in many patients. From a statistical standpoint, it is not clear if the results from our regimen differ from those of this trial, as we have not pressed forward aggressively to continue pursuing a drug-free state in the face of an asymptomatic DSA. We have viewed the appearance of DSA as an unacceptable risk for late graft loss that should be avoided, and opted not to consider immunosuppression elimination without some evidence that monotherapy belatacept has some risk. We reason that the ultimate goal is graft function without side effects, and that risking graft loss in pursuit of an immunosuppressive-free state without evident benefit over a state maintained with a once monthly CoB-based regimen imposes risk without compensatory benefit. Particularly in the absence of a clear metric identifying patients at risk for ABMR and graft loss, we view complete drug withdrawal to be unsupportable at this time.

2 STUDY OBJECTIVES

2.1 Primary Objective

This study will determine whether T-cell depletion followed by belatacept and daily maintenance therapy with sirolimus will permit recipients of renal allografts to avoid rejection and eventually be weaned to belatacept monotherapy maintenance immunosuppression. The primary endpoint will be the number of patients successfully withdrawn from sirolimus for 1 year after their last dose of sirolimus. “Successfully withdrawn” will be defined as a patient off sirolimus without clinical or biopsy evidence of rejection.

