4.2 Analyses

Demographics and Baseline Characteristics

Demographic and baseline characteristics of patients will be summarized descriptively by treatment group, by means and standard deviations (SDs) for continuous variables and frequency distribution for categorical variables. Summaries will be performed based on the data set.

Efficacy Analyses

No formal statistical hypothesis testing will be performed for the primary endpoint. All efficacy analyses will generally be descriptive in nature. The primary efficacy analysis will be to assess the proportion of patients successfully withdrawn from sirolimus for one year. The point estimate of this proportion and the exact two-sided 95% confidence interval (CI) will be provided for each treatment group. A patient will be considered to be successfully withdrawn from immunosuppression for one year if the patient has been administered only belatacept for a period of 365 days, following successful completion of sirolimus, and has not experienced biopsy-proven acute rejection, formation of DSA, or graft loss for this same period of 365 days. Secondary efficacy outcome measures involving incidences and proportions will be descriptively summarized with point estimates and exact, two-sided 95% CIs by treatment group. Other secondary efficacy outcome measures will be descriptively summarized by means and SDs for continuous outcomes and frequency distributions for categorical outcomes.

Safety Analyses

All AEs and SAEs will be summarized by treatment group. Laboratory values will also be descriptively summarized.

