6.2 Maintenance Immunosuppressive Reduction

Beginning any time after year 1 (week 53), participants who are deemed eligible for sirolimus withdrawal as determined by clinical and flow cytometric parameters

(described below) may be withdrawn from sirolimus. Withdrawal will proceed at a maximum rate of 66% of the original dose for 4 weeks, 33% of the original dose for another 4 weeks, then discontinued. However, each reduction in dose will be predicated on stable flow cytometric profile.

Criteria for Sirolimus Withdrawal. Participants will be deemed eligible for withdrawal of sirolimus if they meet all of the following criteria:

1. No episodes of steroid resistant acute rejection since transplant, and no episodes of steroid sensitive rejection for 12 months.
2. Stable renal function, as defined by both of the following:
 - a. GFR, using calculated CrCl (Cockcroft-Gault) of > 40ml/min.
 - b. Creatinine, which in the 12 weeks preceding withdrawal has not increased more than 20% with respect to the lowest creatinine observed during the same period.
 - c. Absence of histologic evidence of acute or chronic rejection on pre-withdrawal renal biopsy according to the Banff criteria for acute, chronic and humoral rejection.
3. Absence of DSA reactivity, as measured by de novo anti-donor-HLA antibodies.
4. ALC at least 80% of the baseline ALC prior to alemtuzumab.
5. Ki67 expression on CD3+ T cells that is within 1 standard deviation of the normal expression in untreated controls. Ki67 is typically seen in <3% of lymphocytes in health controls and a value >5% exceeds the value accepted for purposes of this trial.

For determining eligibility, a renal biopsy will be obtained and creatinine clearance will be estimated. Requisite blood samples will be obtained within two weeks before starting sirolimus withdrawal. Results of laboratory assessments of immune status will be made available to, and reviewed by, the investigator. These data will be reviewed with the knowledge of previous results of immunosuppression withdrawal obtained in the current trial up to the time of review.

Maintenance Immunosuppressive Therapy

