Patients who are weaned from sirolimus will be maintained on belatacept 5mg/kg once per month +/- 3 days indefinitely. In the event that patients are not successfully weaned from sirolimus, long-term maintenance therapy will be established on an individual basis. Patients with subclinical or steroid sensitive rejections can be continued using sirolimus and belatacept, or altered based on the individualized requirements of each patient. This may include the use of CNIs, anti-metabolites, steroids, biologics or other available medications dose to achieve the required therapeutic effect. Patients experiencing steroid resistant TCMR or ABMR will be converted to a CNI-based regimen.

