6.6 Treatment of Rejection

Biopsy proven acute rejection episodes will be treated based on the discretion of the transplant physician or surgeon. It will be permissible but not mandatory to continue protocol participation for patients who experience an early steroid sensitive rejection as described above. Presumed rejection episodes will be confirmed by biopsy as soon as possible after the initiation of symptoms. Biopsies will be performed at the Emory Transplant Clinic if at all possible. If patients are greater than a 24-hour trip from the center, the PI may elect to have the biopsy performed by a qualified transplant physician or surgeon. The Banff grade of rejection will be documented in the clinical case file and the date of the first episode of acute rejection will be the date the rejection is confirmed by biopsy. Management of rejections must be based on biopsy and clinical findings.

Patients with suspected rejection will undergo physical exam, laboratory evaluation, ultrasound examination of the kidney, and percutaneous renal biopsy accompanied by blood collection for peripheral phenotype analysis, transcriptional analysis and evaluation of donor specific alloreactivity. Biopsies will be evaluated by the attending transplant physician and reviewed with a pathologist skilled in the evaluation of renal transplant biopsy material. Biopsies will be evaluated using the Banff criteria for determination of allograft rejection.¹³⁰⁻¹³² Patients with biopsy proven rejection will be treated with methylprednisolone 500mg x 1-3 days. Failure to respond to methylprednisolone in no more than 3 days, or rapid worsening of graft function despite methylprednisolone therapy will prompt use of an approved antilymphocyte agent or other therapies deemed appropriate by the attending transplant physician or surgeon. After treatment of a steroid resistant rejection episode, patients will be discontinued from study treatment/immunosuppressive weaning and returned to a maintenance regimen established at the discretion of the attending transplant physician or surgeon in keeping with standard of care immunosuppression for renal transplantation. After treatment of a steroid sensitive rejection episode, patients may be restarted on the previous level of immunosuppression. The dosing and intensity of the regimen for maintenance

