immunosuppression shall be guided by the attending transplant physician or surgeon, to re-establish clinical stability of renal function. This may result in patients receiving different doses, or restarting previously discontinued medications. Any rescue therapy will prompt a reinstatement of viral, fungal and PCP prophylaxis. The need for additional antilymphocyte agents will be carefully scrutinized by the PI prior to their administration. Alternative therapies will be utilized as appropriate (e.g., plasmapheresis, IVIG) unless it is clear (by biopsy) that the rejection is being mediated by lymphocytes.

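### The section 4.2 success definition scores only the 365 days after sirolimus completion and is not tied to the first withdrawal attempt, so a patient whose first attempt led to a treated rejection can still be counted as a success

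*Combined protocol and SAP*

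**What the plan says.** The primary endpoint is defined twice, in different terms.

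- **Section 2.1:** "The primary endpoint will be the number of patients successfully withdrawn from sirolimus for 1 year after their last dose of sirolimus". Success there "will be defined as a patient off sirolimus without clinical or biopsy evidence of rejection". The rejection clause has no time window. Section 3.3 repeats the last-dose anchor.
- **Section 4.2:** success has a treatment condition, that "the patient has been administered only belatacept for a period of 365 days, following successful completion of sirolimus". It also has an event condition, under which a successful patient "has not experienced biopsy-proven acute rejection, formation of DSA, or graft loss for this same period of 365 days". Here events count only inside that period.

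The rules on what may follow a rejection are elsewhere.

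- **Section 6.2, eligibility for withdrawal:** "No episodes of steroid resistant acute rejection since transplant, and no episodes of steroid sensitive rejection for 12 months". Absence of DSA is also required. Withdrawal may start from week 53, with no closing date.
- **Section 6.2, maintenance:** "Patients with subclinical or steroid sensitive rejections can be continued using sirolimus and belatacept", or the regimen may be altered for the individual patient.
- **Section 6.6:** "After treatment of a steroid sensitive rejection episode, patients may be restarted on the previous level of immunosuppression", and of the maintenance regimen afterwards, "This may result in patients receiving different doses, or restarting previously discontinued medications". Steroid-resistant rejection ends weaning.
- **Section 9.2:** subclinical rejection that has resolved does not by itself rule out weaning, if it arose during homeostatic repopulation.
- **Section 8.1, medication flowchart:** weaning begins during weeks 53 to 104.

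No section limits the number of attempts, names the first attempt as the scored one, or makes a failed attempt final.

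**The concern.** The primary objective is to learn whether patients can avoid rejection and be weaned to belatacept alone. Under section 4.2 as written, two kinds of rejection can escape the primary endpoint. One occurs during the taper, before the 365-day period opens. The other occurs after a first withdrawal and is followed by sirolimus restart and a later wean: the restart creates a new last dose, and the earlier rejection lies before the new period. Either patient meets section 4.2 if the later 365 days are event-free, although the first attempt led to rejection and treatment.

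Under section 4.2, counting a later attempt can add successes but cannot remove any. The study is open-label and single-center, and the attending physician guides the regimen after a rejection, so whether a patient gets a second chance depends on the outcome of the first. The proportion and its exact interval are the main evidence the trial will report.

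**Working it through.** **1. The plan's own figures (sections 3.1 and 3.4).** Twenty enrolled, 20% excluded for rejection, four more ineligible or refusing: 20 − 0.20 × 20 − 4 = 12 attempted. At 50% success, 12 × 0.50 = 6. Both figures reproduce. The exact (Clopper-Pearson) 95% interval for 6/12 is 21.1% to 78.9%.

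**2. Is there time for a second attempt?** Section 3.1 gives at least five years of follow-up, or 260 weeks. The fastest taper in section 6.2 is 4 + 4 = 8 weeks.

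- First taper starts at week 53; last dose 53 + 8 = week 61; suppose rejection at week 62.
- Eligible again after the 12-month look-back: 62 + 52 = week 114.
- Second last dose: 114 + 8 = week 122. One year completed: 122 + 52 = week 174.

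The latest rejection that still leaves room is 260 − 52 − taper − 52: week 148 for an 8-week taper, 143 for 13 weeks and 130 for 26 weeks.

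**3. If the flowchart window were binding.** A steroid-sensitive rejection in the first week of weaning gives 53 + 52 = week 105 as the earliest re-wean, which is past week 104. The re-wean route for steroid-sensitive rejection would be closed. The taper gap would remain, because the section 4.2 period opens only after sirolimus completion. The plan also does not say whether the 12-month look-back applies to resolved subclinical rejection.

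**4. Size.** Let *k* be the number of the 6 first-attempt failures later scored as successes if a further attempt works, and *s* the success rate of that attempt. Expected successes = 6 + *k* × *s*. Neither *k* nor *s* is in the documents, so both are assumptions, shown over a range.

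| *k* | *s* = 0.25 | *s* = 0.50 | *s* = 0.75 |
|---|---|---|---|
| 0 | 6 | 6 | 6 |
| 2 | 6.5 | 7 | 7.5 |
| 4 | 7 | 8 | 9 |
| 6 (not reachable in practice) | 7.5 | 9 | 10.5 |

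**5. Denominator.** Section 4.1 assigns efficacy analyses to all transplanted patients and makes patients with withdrawal attempted a subgroup. With the 20 patients of section 3.1, *k* = 2 and *s* = 0.50 give:

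| Denominator | First attempt only | With re-attempts |
|---|---|---|
| Attempted (12) | 6/12 = 50% (21.1% to 78.9%) | 7/12 = 58.3% (27.7% to 84.8%) |
| All transplanted (20) | 6/20 = 30% (11.9% to 54.3%) | 7/20 = 35% (15.4% to 59.2%) |

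**The case against.** The best reply is that this reads permission into silence. Much of it stands.

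- **A reader might infer that the protocol provides for re-weaning.** It does not. Section 6.6 allows drugs to be restarted to regain stability and says nothing about tapering again. Section 6.2 assigns individual long-term maintenance to patients not successfully weaned, and the sentence on sirolimus plus belatacept follows directly from that. A second wean is left open by the 12-month look-back and the absence of a closing date; it is not planned.
- **A reader might infer that both definitions have the gap.** Section 2.1 alone can be read to fail anyone who rejected. Section 4.2 also requires successful completion of sirolimus, which a rescued taper arguably lacks, but that phrase is undefined. If the strict reading is intended, section 4.2 does not express it.
- **A reader might infer that most failures could be converted, giving 9/12 (75%, interval 42.8% to 94.5%).** That needs all six failures re-weaned. Steroid-resistant rejection ends weaning, DSA fails the eligibility criteria, and the biopsy, creatinine, lymphocyte-count and Ki67 criteria must also be met. The figure is a theoretical ceiling at 50% repeat success.
- **Rejection would not be hidden.** Biopsy-proven acute rejection is a secondary outcome at 1, 3 and 5 years. No hypothesis test is planned, so no error rate is affected.

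What remains is that the operative analysis definition can score such a patient as a success, and nothing in the plan says otherwise.

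**Conclusion.** The point holds for steroid-sensitive rejection and for resolved subclinical rejection. It does not extend to steroid-resistant rejection or DSA, which are barred from re-weaning. Section 4.2 leaves open which attempt is scored and omits the taper, and it is not reconciled with section 2.1. The re-wean route also depends on section 6.2 rather than the section 8.1 window governing when weaning may begin; the two conflict and must be reconciled.

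On the plan's own figures a plausible shift is about one patient, from 6 to 7 successes. That rests on assumed values for the number re-weaned and their success rate, and on reading the planned 50% as a first-attempt rate. The shift is small beside the width of the exact intervals, but it runs in one direction and affects a descriptive proportion that is the trial's primary result. The change should be made.

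**What to change.** Use one definition in the synopsis and in sections 2.1, 3.3 and 4.2:

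- **Anchor:** the first withdrawal attempt, scored from the first sirolimus dose reduction through 365 days after the last dose of that attempt.
- **Failure:** rejection, DSA formation, graft loss, restart of sirolimus or any other added immunosuppression in that period. A first attempt abandoned before a last dose is also a failure. State whether rejection means biopsy-proven only (section 4.2) or clinical or biopsy evidence (section 2.1).
- **Finality:** a later attempt cannot reverse a failure. Report later attempts on a separate descriptive line.
- **Denominator:** state whether the primary proportion is of all transplanted patients or of those in whom withdrawal was attempted.

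Reconcile section 6.2 with the section 8.1 flowchart on when weaning may begin. This review takes no view on which is right, and decisions on restarting or re-weaning stay as they are.

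The cost is wording in four places, with no added visits or patients. Scoring the taper makes the endpoint stricter than section 4.2 now states, and the reported success proportion may be lower.
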